#### 4.3 Gender/Minority/Pediatric Inclusion for Research

We will not exclude potential subjects from participating in this study based on ethnic origin or socioeconomic status. Every attempt will be made to enter all eligible patients in this protocol and therefore address the study objectives in a patient population representative of the entire breast, uterine and cervical cancer population treated at Thomas Jefferson University Hospital. By the nature of the diseases covered in this trial the majority enrolled will be female. We will not exclude male patients with breast cancer.

#### 4.4 Recruitment and Screening

46 subjects will be recruited. No advertisement will be conducted. Screening requirements include serum measurement of creatinine, aspartate aminotransferase, alanine aminotransferase and alkaline phosphatase taken on a non-fasting blood sample. Potential research subjects will be identified by a member of the patient's treatment team, the protocol investigator, or research team at participating centers from Medical Oncology, Radiation Oncology and Surgical offices. Investigators will screen the patient's medical records for suitable research study subjects and discuss the study and their potential for enrolling in the

research study. Patients will be screened based on pathology, image studies etc. A maximum of 23 patients will be enrolled onto each arm of the trial (see Statistical Analysis Plan Section 9).

#### **4.5 Subject Withdrawal/Discontinuation Criteria**

Subjects may withdraw consent at any time for any reason or be dropped from the trial at the discretion of the investigator should any untoward effect occur. In addition, a subject may be withdrawn by the investigator or the Sponsor if enrollment into the trial is inappropriate, the trial plan is violated, or for administrative and/or other safety reasons.

Subjects may be discontinued from the trial for any of the following reasons:

- The subject withdraws consent.
- Documented Disease progression
- Unacceptable adverse experiences as described in Section 8
- Investigator's decision to withdraw the subject
- Noncompliance with trial treatment or procedure requirements
- The subject is lost to follow-up
- Administrative reasons

The End of Treatment and Follow-up visit procedures are listed in Section 6 Trial Flow Chart. After the end of treatment, each subject will be followed for 30 days for adverse event and 90 days for serious adverse events monitoring as (described in Section 8.4).

##### **4.5.1 Subject Replacement Strategy**

Patients who are discontinued from the study for any reason outlined in Section 4.5 will not be considered as evaluable for this study and will be replaced.

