### 10.2 Analysis for primary outcomes.

The primary objective of the study is to assess the impact of metformin and doxycycline on CAV1 expression by immunohistochemistry (IHC) in carcinoma cells. All patients from whom samples are obtained both pre- and post-treatment will be included in the primary analyses. Within-patient change in IHC scores will be analyzed using the Wilcoxon signed-rank test.

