### 10.4 Sample size justification

The sample in each cohort is based on having 80% power to detect an average increase in CAV1 staining of 20% using a one-sided Wilcoxon signed-rank test with  $\alpha=0.05$ . Based on pilot data in other cancers, we assume the standard deviation of change scores to be 32%. A sample size of 19 per cohort is required under these assumptions. Allowing for approximately 15% of patients to have missing pre- and or post-treatment data, we will recruit 23 women per cohort. Cohort 1 will consist of breast cancer patients and cohort 2 will include both uterine and cervical (gynecologic) cancers.

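### Section 4.5.1 makes every discontinued patient non-evaluable and replaces them, which contradicts the paired-sample primary analysis set and the cap of 23 per arm and leaves the DLT count undefined

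*Combined protocol and SAP*

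**What the plan says.** Section 4.5.1 (Subject Replacement Strategy) states: "Patients who are discontinued from the study for any reason outlined in Section 4.5 will not be considered as evaluable for this study". The same sentence requires a replacement for each of them. The reasons listed in Section 4.5 include "Unacceptable adverse experiences as described in Section 8", "Noncompliance with trial treatment or procedure requirements" and "The subject is lost to follow-up", along with withdrawn consent, progression, investigator decision and administrative reasons.

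The primary analysis set is defined differently. Section 10.2 reads: "All patients from whom samples are obtained both pre- and post-treatment will be included in the primary analyses". The Study Summary says the same under both its evaluation criteria and its statistical analysis. Neither place excludes patients for discontinuation.

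Section 4.4 adds: "A maximum of 23 patients will be enrolled onto each arm of the trial". Section 10.4 reaches 23 by taking 19 patients for "80% power to detect an average increase in CAV1 staining of 20" points and adding about 15% for missing tissue. Neither section provides for replacement.

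Section 10.6 indexes its safety boundary by the number of patients enrolled and does not mention evaluability. No safety or DLT-evaluable population is defined anywhere.

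**The concern.** Resection is part of each patient's planned care. A patient withdrawn from the trial for toxicity or noncompliance can therefore still supply a post-treatment sample, and a patient lost to follow-up after surgery has already done so. Section 10.2 analyses these patients; Section 4.5.1 discards and replaces them. No text says which section governs, so the choice could be made after the data are seen.

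Tolerance and adherence are observed after treatment starts. Excluding patients on those grounds leaves the ones who took and tolerated the drugs. In an uncontrolled pre-post comparison with a one-sided test, that probably favours a larger CAV1 increase.

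The same wording raises a safety question. If a patient discontinued for a DLT is not evaluable for the study, it is unclear whether the Section 10.6 count includes that patient.

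**Working it through.** **1. The plan's own figures reproduce.**
- Sample size. Inputs from Section 10.4: mean change 20, SD 32, one-sided alpha 0.05, Wilcoxon signed-rank test. Simulation with exact critical values and normally distributed changes gives power 0.797 at n = 18 and 0.819 at n = 19, so 19 is the smallest n that reaches 80%.
- Inflation. 19 / (1 - 0.15) = 22.4, rounded up to 23.
- DLT boundary. The study stops when P(rate > 0.05), under Beta(0.04 + x, 1.96 + n - x), exceeds 0.90. The posterior is 0.905 at 2/10, 0.889 at 2/11, 0.900 at 3/22, 0.890 at 3/23, 0.901 at 4/35 and 0.893 at 4/36. Every step of the printed table is confirmed. The table's last row is 36; the same formula keeps the boundary at 5 through 46 (0.919 at 5/46).

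None of these figures is in dispute.

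**2. Who is in the primary set.**

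| Patient withdrawn from the trial | Section 10.2 | Section 4.5.1 |
|---|---|---|
| Toxicity, paired tissue available | in | out, replaced |
| Noncompliance, paired tissue available | in | out, replaced |
| Lost to follow-up after surgery, paired tissue available | in | out, replaced |
| Any reason, no pair | out | out, replaced |

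**3. Enrolment.** Once an arm has enrolled 23, one replacement makes 24, above the Section 4.4 maximum. If replacement did deliver 23 evaluable patients, simulated power would be about 0.88 rather than 0.82.

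**4. Direction of the efficacy bias.** Let q be the share of paired patients who were discontinued, m_c the mean change in completers and m_d the mean change in discontinued patients. The all-paired mean is (1 - q)m_c + q·m_d, so analysing only evaluable patients overstates it by q(m_c - m_d). The documents give neither q nor m_d. The difference is zero if m_d = m_c. For illustration only, q = 20%, m_c = 20 and m_d = 0 give 0.8 × 20 = 16, a difference of 4 points.

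**5. What would happen to the stopping rule if 4.5.1 were applied to it.** One patient can decide the outcome: 2 DLTs in 10 gives a posterior of 0.905 and stops the study. If one of those two is replaced by a patient without a DLT, 1/10 gives 0.589 and the study continues.

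Over the whole trial, suppose a share f of DLT patients is removed and replaced. The DLT rate among counted patients becomes p(1 - f)/(1 - pf). For p = 0.15 and f = 0.5 this is 0.075/0.925 = 8.1%. An exact recursion of the Section 10.6 boundary, checked after every patient from 10 to 46, gives the probability of stopping:

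| True DLT rate | f = 0 | 10% | 25% | 50% | 75% |
|---|---|---|---|---|---|
| 10% | 0.62 | 0.54 | 0.42 | 0.20 | 0.05 |
| 15% | 0.89 | 0.84 | 0.74 | 0.46 | 0.13 |

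Three assumptions are not in the documents: the value of f, pooling the two cohorts to 46, and retaining boundary 5 for 36 to 46 patients. Section 10.1 says analyses are by cohort. The same recursion stopped at 23 patients gives 0.70 at a true rate of 15% with nobody removed, and 0.32 at f = 50%.

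**The case against.** The strongest reply concerns safety. A reader might infer that 4.5.1 takes DLT patients out of the stopping rule. The documents do not say so. Section 10.6 counts enrolled patients, so read alone it keeps them in numerator and denominator. Section 5.2.5 counts DLTs to 30 days after therapy, Section 6.5 follows patients withdrawn for adverse events until resolution or stabilisation, and Section 8.4.2 sends all adverse events to the DSMC. A DLT also does not always end treatment: under Section 5.2.1 a related grade 3 toxicity interrupts it and may allow resumption. This stands. The loss of DLT patients is a risk from unreconciled text, and the table above is conditional on it.

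A reader might also infer that anyone who stops the drugs falls under 4.5.1. Section 5.2.1 speaks of stopping treatment and Section 4.5 of leaving the trial, and the protocol never links or separates the two. The contradiction is certain only for patients withdrawn from the trial who still supply tissue.

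It is tempting to say that replacement duplicates the 15% allowance. The overlap is only partial. The allowance is for missing tissue, and baseline tissue is collected only when available (study calendar, Section 6), so a pair can be missing without any discontinuation.

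Finally, the efficacy bias arises only if 4.5.1 overrides 10.2, and a specific inflation of the CAV1 effect would only restate invented inputs. That is also correct. None of these replies removes the contradiction with 10.2 or with the cap.

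**Conclusion.** The conflict between 4.5.1 and both the paired-sample primary set and the maximum of 23 per arm is established from the text. If 4.5.1 were followed, the primary set would be selected on tolerance and adherence. The probable direction is towards a larger CAV1 change; the size cannot be derived from the documents.

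For safety, the finding is an undefined population, not a stated exclusion. Were 4.5.1 applied to the DLT count, the loss of stopping probability would range from modest (0.89 to 0.84 at a true rate of 15%, f = 10%) to severe (0.13 at f = 75%), under the assumptions in the working. The sample size of 19, the recruitment target of 23 and the DLT boundaries need no change.

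**What to change.** Rewrite Section 4.5.1 to state that:

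- (a) every patient with paired tissue stays in the primary analysis whether or not treatment was completed, subject to the consent terms on using samples and data after withdrawal (Section 11.1 addresses revoked authorization);
- (b) every patient who takes at least one dose stays in the safety set and in the numerator and denominator of the Section 10.6 rule;
- (c) replacement is limited to patients who never start study drug, or is otherwise reconciled with the cap in Section 4.4. The 15% allowance already covers missing pairs, which overlap partly with discontinuations. If (c) is kept strict, the amendment should also say what happens to a patient enrolled with suspected cancer whose resection shows none.

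State whether stopping drug under Section 5.2.1 counts as discontinuation under Section 4.5. Report a completers-only analysis as a sensitivity analysis.

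The cost is a one-paragraph amendment with no new data collection. The reported effect may be slightly less favourable.

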## **5 Study Treatments**

### **5.1 Study Product**

The investigator shall take responsibility for and shall take all steps to maintain appropriate records and ensure appropriate supply, storage, handling, distribution and usage of investigational product in accordance with the protocol and any applicable laws and regulations.

### **5.2 Study Product Description**

#### Metformin:

Metformin is a biguanide drug currently approved for the treatment of type 2 diabetes mellitus by the FDA. It is currently being investigated in multiple cancer treatment trials.

Metformin is the therapeutic agent in the protocol. The initial starting dose will be 500mg orally daily for 3 days which then will be increased to 500 mg twice daily and, if tolerated, further increased to 1000mg twice daily after day 6. Patients will maintain 1000 mg twice a day dosing until the day prior to their scheduled definitive surgery. This dose schedule has been shown to be well tolerated and was able to promote cellular changes consistent with beneficial anti-cancer effects in breast cancer patients (32).

The treatments to be used in this trial are outlined below in Table 2. Trial treatment should begin within 5 days of eligibility confirmation.

**Table 2 Trial Treatments**

Drug	Dose Level	Dose	Route of Administration	Regimen
Metformin	-1 1 2	500 mg QDay 500 mg BID 1000 mg BID	Orally	Day 1-3 Day 4-6 Day7- Day Before Surgery
Doxycycline	-1	100 mg Q12 hours	Orally	Day 1- Day Before Surgery

#### Doxycycline:

Doxycycline is an antibiotic provided in the formulation doxycycline hyclate. Doxycycline is virtually completely absorbed after oral administration. Following administration of a single 200 mg dose to adult volunteers, average peak serum doxycycline levels were 2.6 mcg/mL at 2 hours, decreasing to 1.45 mcg/mL at 24 hours. The mean Cmax and AUC 0-∞ of doxycycline are 24% and 13% lower, respectively, following single dose administration of DORYX tablets, 100 mg with a high fat meal (including milk) compared to fasted conditions. The mean Cmax of doxycycline is 19% lower and the AUC 0-∞ is unchanged following single dose administration of DORYX Tablets, 150 mg with a high fat meal (including milk) compared to fasted conditions. The clinical significance of these decreases is unknown.

Tetracyclines are concentrated in bile by the liver and excreted in the urine and feces at high concentrations and in a biologically active form. Excretion of doxycycline by the kidney is about 40%/72 hours in individuals with a creatinine clearance of about 75 mL/min. This percentage may fall as low as 1-5%/72 hours in individuals with a creatinine clearance below 10 mL/min.

Studies have shown no significant difference in the serum half-life of doxycycline (range 18-22 hours) in individuals with normal and severely impaired renal function. Hemodialysis does not alter the serum half-life.

Doxycycline is an FDA approved product that is indicated for the prophylaxis against and treatment of both bacterial and protozoal infections. For adults the dose is 200 mg on the first day of treatment administered as 100 mg every 12 hours followed by a maintenance dose of 100 mg daily. The maintenance dose may be administered as a single 100 mg dose of 50 mg dose every 12 hours. Serious infections are treated with a sustained dose of 200 mg per day in divided doses. Treatment for uncomplicated bacterial infections typically lasts for 7 days total. Prophylaxis for malaria can be continued daily for the period of time the patient is in a malarious area and continued for 4 weeks thereafter, up to 4 months.

#### **5.2.1 Dose Calculation**

##### **Rules for dose modification: Toxicity monitoring, dose modification and treatment of complications:**

Particular attention will be paid in the first three days of treatment. Patients will take 500mg/day for 3 days. If tolerated, starting day 4, patients will increase to 500mg twice daily. If this dose increase is tolerated, then on day 7 the patient will be dose escalated to 1000mg twice daily. The maximum tolerated dose will be taken until the day before surgery with food. A phone call on or around the day of each dose escalation (± 2 days) will be made in order to evaluate the tolerability of the drug and also weekly thereafter. Patients will be instructed to contact the clinical investigators should any toxicity occur during the study (66).

Metformin will be held for 12 hours if CAT scan intravenous contrast is administered to decrease risk of lactic acidosis. This approach is more stringent than the most recent recommendation of the American College of Radiology which does not recommend holding metformin in the absence of comorbidities (renal insufficiency, liver dysfunction, alcohol abuse, cardiac failure, myocardial or peripheral muscle ischemia, sepsis or severe infection) which are exclusion criteria for this clinical trial (29).

Toxicity will be evaluated using the NCI Common Terminology Criteria for Adverse Events (CTCAE) version 4.03.

- Grade 1 toxicity: Patient will be maintained on full dose.
- Grade 2 toxicity (probably or definitely drug related): Dose will be reduced back to the maximum tolerated dose until grade 1 or lower. If symptoms are not resolved within 3 days the treatment will be discontinued definitively.
- Grade 3 toxicity (probably or definitely drug related): Treatment will be interrupted and toxicity reassessed daily. If toxicity improves to grade 2, dose will be reduced back to the maximum tolerated dose.
- Grade 4 toxicity (probably or definitely drug related): Treatment will be discontinued definitively.

In case of grade 1 or 2 diarrhea (the most frequent side effect) a concomitant administration of loperamide may be provided, and dose may be reduced back to the maximum tolerated dose or temporarily halted at the treating physician's discretion. Clear documentation of this will be recorded in the patient's research chart.

If patient experiences continued intolerable side effects, dose management may be discussed with a study investigator and dose modification can be recommended as needed. Clear documentation of this will be recorded in the patient's research chart.

If doses of either medication are missed due to toxicity they should not be replaced. If a dose is not taken due to an error, it may be taken up to 6 hours later. If vomiting occurs within 30 minutes of intake, that dose may be repeated. These events should be recorded by the patient on their pill diary.

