**Target**

**Population:**

- Patients aged 18 years and above
- Known or suspected breast, uterine (endometrial cancer with histologies including endometrioid, serous, clear cell and carcinosarcoma), or cervical cancer.

- Have surgical intent for resection as a part of their planned therapy
- Performance status ECOG 0-1
- Normal organ function including creatinine <1.5

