### **1.4.2 Potential Risks**

#### Metformin

Metformin's most serious toxicity is lactic acidosis, occurring in three of 100,000 patient-years of use. Risk is significantly reduced when metformin use is avoided in those patients with hepatic, cardiac, or renal compromise. However, metformin's risk of lactic acidosis may be overstated since the recent evaluation of metformin associated lactic acidosis cases from 347 trials showed that the risk of lactic acidosis with metformin was not significantly increased compared with

other antiglycemic agents (88). Minor gastrointestinal upset is the most common toxicity, leading to cessation of therapy in less than 5% of individuals. Metformin does not induce hypoglycemia.

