### 4.2 Subject Exclusion Criteria

The subject must be excluded from participating in the trial if the subject:

1. Received any prior cancer therapy for the breast, uterine, or cervical cancer that is being resected, including progesterone therapy for endometrial cancer patients.
  - a. Patients may have had prior therapy for other contra-lateral breast cancer.
2. Subjects who are pregnant or breastfeeding or may become pregnant during metformin and doxycycline administration.
3. Subjects on metformin or doxycycline for any reason during the preceding 4 weeks.
4. Diabetic subjects that are managed by taking metformin or insulin.
5. Subjects who have received iodinated contrast dye must wait 12 hours prior to starting Metformin. If a CT scan with contrast is scheduled after screening and consent, the

metformin cannot be taken until after the CT with contrast has been completed and they have waited 12 hours.

6. Patients with serum creatinine level greater than 1.5 mg/dL.
7. Patients with history of lactic or any other metabolic acidosis.
8. Patients with history of congestive heart failure stage III or greater.
9. Patients scheduled for definitive cancer surgical resection less than 7 days from beginning of study drug administration or greater than 5 weeks from beginning study drug administration.
10. Patients with history of hepatic dysfunction or hepatic disease and abnormal liver function tests defined as AST, ALT, Alk Phos, and or total bilirubin greater than 2.5 times the upper limit of normal.
  - a. Patients who have a history of hepatic dysfunction or hepatic disease and normal liver function tests will be eligible to participate.
11. Patients with a current history (in the past 30 days) of heavy drinking which is defined in accordance with CDC definition as more than 8 drinks per week for women and more than 15 drinks per week for men. A standard drink contains .6 ounces of pure alcohol. Generally, this amount of pure alcohol is found in 12-ounces of beer, 8-ounces of malt liquor, 5-ounces of wine, 1.5-ounces or a "shot" of 80-proof distilled spirits or liquor (e.g., gin, rum, vodka, or whiskey). While on study, patients should limit their alcohol consumption to no more than 8 drinks per week for women and no more than 15 drinks per week for men. Patients who feel they cannot comply with this recommendation are not eligible. Prior allergic reaction to metformin, doxycycline, or any other tetracycline antibiotic in the past.

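### Section 5.2.1 says six comorbidities are exclusion criteria, but Section 4.2 fully excludes only two, covers two in part and omits two (a minor safety-consistency correction)

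*Combined protocol and SAP*

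**What the plan says.** Section 5.2.1 sets the contrast rule: "Metformin will be held for 12 hours if CAT scan intravenous contrast is administered to decrease risk of lactic acidosis". It then calls this stricter than a radiology recommendation which, as the protocol describes it, asks for no hold when certain comorbidities are absent. Six are listed: renal insufficiency, liver dysfunction, alcohol abuse, and then "cardiac failure, myocardial or peripheral muscle ischemia, sepsis or severe infection) which are exclusion criteria for this clinical trial".

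The operative criteria are in Sections 4.1 and 4.2. For the heart, item 8 of 4.2 reads "Patients with history of congestive heart failure stage III or greater". For the liver, item 10 begins "Patients with history of hepatic dysfunction or hepatic disease and abnormal liver function tests" and defines abnormal as more than 2.5 times ULN; item 10a adds "Patients who have a history of hepatic dysfunction or hepatic disease and normal liver function tests will be eligible to participate". Item 6 excludes raised creatinine, item 7 a history of lactic or other metabolic acidosis, and item 11 heavy drinking in the past 30 days. The Study Summary also has a general line under Target Population: "Normal organ function including creatinine <1.5".

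On why such patients matter, Section 1.4.2 says "Risk is significantly reduced when metformin use is avoided in those patients with hepatic, cardiac, or renal compromise". It adds that the risk may be overstated, citing an evaluation of 347 trials.

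**The concern.** The sentence in 5.2.1 is part of a safety argument. The comparison with the radiology recommendation applies, on the protocol's own description, to patients without the six comorbidities. If some of those patients can enrol, the comparison does not cover them. An investigator reading 5.2.1 would also assume that eligibility screening had removed patients whom a checklist built from Section 4.2 lets through. At stake is agreement between the eligibility text and the dosing-safety text on who may take metformin at up to 1000 mg twice daily.

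**Working it through.** **Step 1. Compare the list in 5.2.1 with the criteria.**

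| Comorbidity named in 5.2.1 | Matching criterion | Covered? |
|---|---|---|
| Renal insufficiency | 4.2 item 6 (creatinine above 1.5 mg/dL); 4.1 item 5 | Yes |
| Alcohol abuse | 4.2 item 11 (heavy drinking, past 30 days) | Yes |
| Cardiac failure | 4.2 item 8, stage III or greater only | In part |
| Liver dysfunction | 4.2 item 10, hepatic history with tests above 2.5 x ULN; 10a admits a hepatic history with normal tests | In part |
| Ischemia, myocardial or peripheral muscle | None | No |
| Sepsis or severe infection | None | No |

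The count is 2 covered, 2 covered in part and 2 absent, of 6.

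**Step 2. Look for other text that closes the gap.** Item 7 concerns past acidosis and names neither omitted condition. The organ-function line in the Study Summary is general, names only creatinine, and is not carried into 4.1 or 4.2. Performance status 0-1 and planned surgery make sepsis at entry unlikely, but they are not criteria for ischemia or infection. Antibiotic use does not keep an infected patient out either: Section 5.4.2 lists cephalexin and penicillin as Class C, which is allowed when established at baseline.

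**Step 3. How many patients could be involved?** The documents give no frequency for the two omitted conditions. Assume 1%, 5% or 10% of those enrolled:

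- Whole trial: 46 x 0.01, 0.05, 0.10 = 0.46, 2.3, 4.6 patients.
- Per cohort: 23 x the same = 0.23, 1.15, 2.3 patients.

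**Step 4. What is the expected effect on lactic acidosis?** Inputs: 3 cases per 100,000 patient-years (Section 1.4.2); 46 patients; 21 days, the site's average time from diagnosis to surgery, and 35 days, the maximum exposure (Section 1.2, dosage rationale).

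Expected cases = patients x days / 365 x rate.

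- 21 days: 46 x 21/365 = 2.65 patient-years; x 3/100,000 = 0.00008.
- 35 days: 46 x 35/365 = 4.41 patient-years; x 3/100,000 = 0.00013.

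The rate in patients with ischemia or sepsis is not given. As a deliberately extreme assumption, apply 100 times the general rate to all 46 patients: 0.008 and 0.013 expected cases.

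**The case against.** The strongest reply is that nothing done to a patient depends on the faulty clause. The 12-hour hold applies to everyone given intravenous contrast, with or without a comorbidity; the clause only supports a comparison. That stands, and no fault in the hold is shown.

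It can also be said that the liver shortfall is narrow. A hepatic history with normal tests need not be current dysfunction, liver tests are required at screening, and Section 7.3 requires screening results to be found acceptable before enrollment. This reduces the practical gap. It does not make the blanket statement in 5.2.1 true, and it does not touch ischemia or infection.

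A reader might infer two further faults that the documents do not support.

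- **A contradiction over contrast.** Iodinated contrast is in the Class D list under item 12, and Section 5.4 bars drugs prohibited by the exclusion criteria, while item 5 permits contrast with a 12-hour wait. But Class D is defined as a prompt to consider modifying therapy, and item 5, in the same section, supplies that modification. Section 5.4 also says that discontinuation may be required when a listed drug is clinically indicated, which is not an automatic ban.
- **No way to stop metformin if either condition arises on study and is judged unrelated.** The graded rules in 5.2.1 do turn on drug-relatedness, for example "Grade 3 toxicity (probably or definitely drug related): Treatment will be interrupted and toxicity reassessed daily". But Section 4.5 lets the investigator withdraw a subject for any untoward effect or other safety reason, whatever the cause, and Section 13.7 has the medical monitor review serious events as they are reported. A mandatory stop rule would be a new preference; its absence is not an error.

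**Conclusion.** The point holds as an inconsistency between two sections: 5.2.1 claims six exclusions, of which 4.2 delivers two in full, two in part and two not at all. That count comes from the text alone and needs no assumption.

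The practical gap is mainly a patient with current ischemia, heart failure below stage III, or a hepatic history with tests not above 2.5 x ULN. The expected effect on lactic acidosis is very small: about 0.0001 cases at the protocol's rate, and at most about 0.013 under the assumed 100-fold rate. The numbers of patients affected rest wholly on the assumed 1% to 10% range. The primary and secondary marker analyses are unaffected. This is a minor safety-consistency correction, worth making because it is cheap and the present statement is wrong as written. It is not evidence that the trial is unsafe.

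**What to change.** 1. In Section 4.2, add two exclusions: current ischemia (myocardial or peripheral muscle), and current sepsis or severe infection. Restricting both to current disease avoids excluding patients for a remote history.
2. In Section 5.2.1, reword the sentence to give the limits actually in force: heart failure excluded from stage III (item 8); a hepatic history excluded when liver tests exceed 2.5 x ULN, and eligible when tests are normal (items 10 and 10a). It should no longer imply that all cardiac failure and all liver dysfunction are excluded.

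Items 8 and 10 and the 12-hour hold can stay as they are. Rewording 5.2.1 alone would make the text true, but it would leave eligible two groups that the dosing section assumes are absent. A cross-reference from the contrast entry in item 12 to item 5 is optional tidying.

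Cost: one protocol amendment and a revised eligibility checklist. If 1%, 5% or 10% of candidates became ineligible (assumption), the extra screening needed to enrol 46 would be 46/0.99 - 46 = 0.5, 46/0.95 - 46 = 2.4, or 46/0.90 - 46 = 5.1 candidates. No visit, blood draw or laboratory test is added, and the sample size does not change.
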